Safety: The primary variables of interest for safety/tolerability are serious vaccine-related adverse experiences, if any occur, and severe, injection-site adverse experiences. Unless they are considered serious adverse events, reports of injection-site adverse experiences will only be solicited from subjects participating in the nonserious adverse experience substudy and from subjects enrolled in the United Kingdom. Subjects from any study site may spontaneously report such events, however.

Efficacy: The primary variable of interest for efficacy is the combined incidence of HPV 16-related CIN 2/3 or worse and HPV 18-related CIN 2/3 or worse. This endpoint will occur if on any single biopsy, endocervical curettage (ECC) or Loop Electrosurgical Excision Procedure (LEEP)/conization tissue block, the following occur:

- Pathology panel consensus diagnosis of: CIN 2, CIN 3 (including squamous carcinoma in situ), adenocarcinoma in situ, invasive squamous cervical carcinoma, or invasive adenocarcinoma of the cervix,

AND

- Detection of HPV 16 and/or HPV 18 by biopsy Thinsection PCR in an adjacent section from the same tissue block.

Of secondary interest are the incidences of colposcopic biopsy and definitive excisional cervical procedures (LEEP, laser conization, cold-knife conization) performed due to HPV 16- and 18-related cervical disease and the overall incidence of ALL CIN 2/3 and invasive cervical cancer (caused by any vaccine or non-vaccine HPV type).

Immunogenicity (Consistency Lot Substudy): For immunogenicity, the following endpoints are of primary interest: (1) the percentage of subjects who achieve anti-HPV 6 ≥ 200 mMU/mL, anti-HPV 11 ≥ 200 mMU/mL, anti-HPV 16 ≥ 200 mMU/mL, and anti-HPV 18 ≥ 200 mMU/mL at Week 4 Postdose 3 and (2) the geometric mean titers (GMTs) to HPV 6, 11, 16, and 18 at Week 4 Postdose 3. Of secondary interest are the GMTs to HPV 6, 11, 16, and 18 at Months 24 and 48. The anti-HPV 6, 11, 16, and 18 responses at Months 7, 24, and 48 will only be measured in the subjects participating in the consistency lot substudy.

Additional exploratory efficacy and immunogenicity endpoints will be summarized. These endpoints are described in the main body of the Data Analysis Plan in Section III.A. for efficacy and Section IV.A. for immunogenicity.

Data Analysis and Decision Criterion for Success of the Study

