Of primary exploratory interest is the overall incidence of ALL CIN 2/3 and invasive cervical cancer (caused by any vaccine or non-vaccine HPV type). Several other exploratory endpoints will be evaluated including: (1) CIN 2/3 or worse related to HPV 16 and 18 separately; (2) vaccine-type-HPV-related CIN 1 or worse; (3) CIN 1 or worse due to any cause; (4) HPV 6/11-related genital warts; (5) any HPV 6/11/16/18-related lesion; (6) any HPV-related lesion; (7) colposcopy; (8) colposcopic biopsy due to any CIN; (9) definitive therapy due to any CIN; and (10) Pap abnormalities. In addition, the antibody responses in vaccine recipients who have breakthrough cases of HPV 16/18-related CIN 2/3 or worse will be evaluated. The potential therapeutic effects of administering the quadrivalent HPV (Types 6, 11, 16, 18) L1 VLP vaccine to subjects who are already infected at baseline with a vaccine HPV type, but who have not yet mounted an immune response to the HPV infection, will be assessed. The time-to-event (or disease-free time) distributions in the vaccine and placebo groups will be compared. Finally, an observational assessment of a potential waning in vaccine efficacy will be performed.

B. Study Participant Populations for Efficacy Analyses

Four patient populations will be considered for the efficacy analyses: 1 per-protocol population and 3 modified intention-to-treat (MITT) populations.

B. Study Participant Populations for Efficacy Analyses (Cont.)

The efficacy analysis using the per-protocol population will be the primary analysis. Supplemental analyses of the primary and secondary efficacy endpoints will be provided using the 3 MITT populations. The populations that will be considered for the exploratory efficacy endpoints are described in their respective sections.

The per-protocol and MITT populations differ with regard to the inclusion/exclusion of protocol violators who are described below.

Per-Protocol Population

To be included in the per-protocol analyses, subjects must:

1. receive all 3 injections with the correct dose of the correct clinical material;
2. be seronegative by RIA to the appropriate HPV types before the first injection and PCR-negative to the appropriate HPV types through Month 7;
3. not receive any nonstudy inactivated vaccine within 14 days of a study vaccine or any nonstudy live virus vaccine within 21 days before or 14 days after a study vaccine;

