In addition, a sensitivity analysis will be performed in which cervical biopsies and tissue specimens collected outside the study (i.e., not according to protocol-specified procedures) are included in the primary efficacy analysis if they meet the case criteria. A cervical biopsy or tissue specimen collected outside the study will be eligible to be counted as an endpoint for this analysis *only* if HPV 16 and 18 PCR results *and* a pathology panel diagnosis are available for the specimen.

2. Secondary Efficacy Analysis

The efficacy of the quadrivalent HPV (Types 6, 11, 16, 18) L1 VLP vaccine in reducing the incidence of: (1) colposcopic biopsy performed due to HPV 16- and 18-related cervical disease; (2) definitive excisional cervical procedures (LEEP, laser conization, cold-knife conization) performed due to HPV 16- and 18-related cervical disease; and (3) either colposcopic biopsy or definitive excisional cervical procedures performed due to HPV 16- and 18-related cervical disease will be estimated using the same methodology that will be used for the primary analysis.

3. Exploratory Efficacy Analyses

a. CIN 2/3 Due to Any HPV Type

The efficacy of the quadrivalent HPV (Types 6, 11, 16, 18) L1 VLP vaccine in reducing the overall incidence of ALL CIN 2/3 and invasive cervical cancer (caused by any vaccine or non-vaccine HPV type) will be estimated using the same methodology that will be used for the primary analysis. Only the point estimate of the vaccine efficacy and a 95% confidence interval for the efficacy with respect to this endpoint will be provided. No statistical testing will be conducted as there will be insufficient power to draw conclusions regarding this endpoint from the cases that are likely to be observed.

It is expected that all subjects will be included in the population at risk for the “all CIN 2/3” endpoint, since almost all subjects should be eligible to be an endpoint with respect to at least 1 of the 13 high-risk HPV types for which subjects are being tested.

C. Approaches to Efficacy Analysis (Cont.)

As a supplement to the “all CIN 2/3” evaluation, the (b)(4) swabs collected from subjects at Months 24, 36, and 48 may be tested (if resources permit) for non-vaccine HPV types by PCR in order to assess the potential “replacement” of HPV types in CIN 2/3 lesions as a result of vaccination. The swabs would likely only be analyzed in subjects who developed CIN 2/3.

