to all CIN (any grade due to any cause) will be estimated. Point estimates and confidence intervals for the vaccine efficacy will be provided using the methodology described above for the primary analyses. The HPV 16- or 18-related CIN 1 or worse endpoint and the HPV 6/11/16/18-related CIN 1 or worse endpoint will be summarized in the per-protocol and the first MITT population. To be included in the analysis of CIN due to any cause, subjects will be required to be seronegative and PCR negative from Day 1 through Month 7 for relevant HPV types or have normal Pap test results from Day 1 through Month 7 and a history of normal Pap test results (see Section III.B.). Only point estimates of the vaccine efficacy and 95% confidence intervals for the efficacy with respect to these endpoints will be provided. No statistical testing will be conducted.

f. Other HPV-Related Lesions

The impact of the vaccine on other HPV-related lesions and other combinations of HPV-related lesions will also be evaluated. The person-time based incidences of: (1) HPV 6- or 11-related external genital warts; (2) any HPV 6, 11, 16, or 18-related lesion; and (3) any HPV-related lesion will be estimated by treatment group. Corresponding 95% confidence intervals for the incidence rates will be provided. To be eligible to be counted as an HPV 6/11-related endpoint, subjects will be required to be seronegative at Day 1 and PCR negative from Day 1 through Month 7 for HPV 6 and HPV 11. To be eligible to be counted as an HPV 16- or 18-related endpoint, subjects will be required to be seronegative at Day 1 and PCR negative from Day 1 through Month 7 for the relevant type. To be eligible to be counted as an endpoint related to other HPV types, subjects will be required to be PCR negative from Day 1 through Month 7 for the relevant HPV types or have normal Pap test results from Day 1 through Month 7 and have a history of normal Pap test results (see Section III.B.). Only point estimates of the incidence rates and 95% confidence intervals for the rates with respect to these endpoints will be provided. No statistical testing will be conducted.

g. Gynecologic Procedures

The efficacy of the quadrivalent HPV (Types 6, 11, 16, 18) L1 VLP vaccine in reducing the incidence of: (1) colposcopy, (2) colposcopic biopsy due to any CIN, and (3) definitive therapy due to any CIN will be estimated using the same methodology that will be used for the

C. Approaches to Efficacy Analysis (Cont.)

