Protocol 015 requires pelvic examinations which include an examination for genital warts. A genital wart examination introduces the potential for ascertainment bias in this study. Subjects are triaged to colposcopy and biopsy based on the results of the Pap tests performed approximately every year. However, in clinical practice, colposcopy is frequently performed based solely on a discovery of genital warts as well. Since a quadrivalent HPV (Types 6, 11, 16, and 18) L1 VLP vaccine is being administered, this could introduce bias if the vaccine is efficacious against genital warts. If the vaccine is efficacious against genital warts, warts will be found more often in the placebo recipients than in the vaccine recipients. Thus, the placebo recipients will be referred for colposcopy more often than the vaccine recipients, and, consequently, more CIN lesions will be detected in these subjects. This may cause the vaccine to appear more efficacious against CIN than it really is. To avoid this type of ascertainment bias, cases of CIN 2/3 or worse that are detected during a colposcopy that was performed *solely* based on a finding of genital warts (i.e., without an accompanying abnormal Pap test result) will not be included in the primary or secondary analyses outlined in this DAP, nor will these CIN cases count toward the total number of cases needed to trigger the analyses. Sensitivity analyses will be performed in which all cases of CIN 2/3 or worse are included regardless of the reason the colposcopy was performed. The Pap test result that will be considered in determining whether or not the colposcopy was performed based on a genital wart finding only will be the Pap test result from the most recent *scheduled* visit prior to the colposcopy date or on the colposcopy date. Pap test results from unscheduled visits at which colposcopies were performed will not be considered because they also represent data that could be influenced by the vaccine's impact on the genital wart endpoint.

D. Statistical Methods (Cont.)**2) Censoring Due to Definitive Therapy**

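### The wart-only colposcopy exclusion is narrower than the bias the plan describes: it names only CIN 2/3 or worse, and only the primary and secondary analyses

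*SAP*

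**What the plan says.** SAP VII.D.1.e.1 sets out the mechanism. Women should reach colposcopy through their Pap results, but in practice warts alone often prompt it. If the vaccine prevents warts, that happens more often on placebo, and more CIN is found there. The plan states the consequence without any grade limit: "This may cause the vaccine to appear more efficacious against CIN than it really is".

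The remedy concerns "cases of CIN 2/3 or worse that are detected during a colposcopy that was performed" for a wart finding alone, judged by the Pap result from the latest scheduled visit. Such cases "will not be included in the primary or secondary analyses outlined in this DAP", and they do not count toward the number that triggers an analysis. The accompanying sensitivity analysis puts them back: "Sensitivity analyses will be performed in which all cases of CIN 2/3 or worse are included regardless of the reason the colposcopy was performed".

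The endpoints that could be touched are these:

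- **Secondary (III.C.2):** "colposcopic biopsy performed due to HPV 16- and 18-related cervical disease", the matching excision endpoint, and either of the two. None carries a CIN grade.
- **Exploratory lesions (III.C.3.e):** efficacy against HPV 16/18-related CIN 1 or worse, against HPV 6/11/16/18-related CIN 1 or worse, and with respect "to all CIN (any grade due to any cause) will be estimated".
- **Exploratory procedures (III.C.3.g):** colposcopy, and biopsy or definitive therapy due to any CIN.
- **ALL CIN 2/3:** III.A says "Of primary exploratory interest is the overall incidence of ALL CIN 2/3 and invasive cervical cancer", and I.B.5 also lists it as exploratory. The Executive Summary (Endpoints) places "the overall incidence of ALL CIN 2/3 and invasive cervical cancer" among the endpoints of secondary interest.

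**The concern.** The plan describes a bias that acts on CIN of every grade and then prescribes a remedy for one grade band in two tiers of analysis. The endpoints left outside are the ones most open to it. Detection of CIN 1 and of CIN of any type depends heavily on how often a woman is examined by colposcopy. If the rule is applied as written, prevention of warts could appear as part of the estimated efficacy against cervical lesions. No analysis in the plan removes wart-only CIN 1.

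**Working it through.** **Step 1. Scope of the rule against scope of the bias (VII.D.1.e.1).**

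| | Bias as described | Exclusion | Sensitivity analysis |
|---|---|---|---|
| Lesion grade | CIN, no grade limit | CIN 2/3 or worse | CIN 2/3 or worse |
| Analyses | not limited | primary and secondary | not specified |

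**Step 2. The rule applied endpoint by endpoint.**

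- Primary endpoint and case trigger: covered.
- By-type summaries (III.C.3.b) and time-to-event analysis (III.C.3.c): both are defined on the primary endpoint, so they plausibly inherit its case set.
- Secondary biopsy endpoint: wart-only CIN 2/3 is removed and wart-only CIN 1 is not. I.B.1 says a lesion seen at colposcopy is biopsied, so CIN 1 specimens will arise. That they fall under cervical disease is an inference, because the term is not graded, but it is the natural one.
- Secondary definitive-therapy endpoint: mostly covered, because VII.D.1.e.2 says referral is typically for a central-laboratory diagnosis of CIN 2 or worse.
- Exploratory CIN 1-or-worse and all-CIN endpoints: no text applies the rule. Read literally, the same wart-only HPV 16 CIN 2 case is dropped from the primary endpoint but counted in HPV 16/18-related CIN 1 or worse.
- ALL CIN 2/3: covered if secondary (Executive Summary), not covered if exploratory (I.B.5, III.A).

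**Step 3. Size.** The SAP gives no figure for wart-only detection, so there is nothing of the plan's to reproduce on this point. Let f be the share of placebo cases found only through wart-only colposcopy, VEw the efficacy against warts and VE the true efficacy against the lesion. f and VEw are assumptions, and the true VE values are illustrative. Wart-only detection in the vaccine group falls by the factor (1 − VEw), so

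apparent VE = 1 − (1 − VE) × [(1 − f) + f × (1 − VEw)],

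and the overstatement is (1 − VE) × f × VEw.

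| True VE | VEw | f = 2% | f = 5% | f = 10% | f = 20% |
|---|---|---|---|---|---|
| 90% | 90% | 90.2% | 90.5% | 90.9% | 91.8% |
| 20% | 90% | 21.4% | 23.6% | 27.2% | 34.4% |
| 20% | 50% | 20.8% | 22.0% | 24.0% | 28.0% |

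Worked corners at VEw = 90%:

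- True VE 90%: 0.10 × 0.02 × 0.90 = 0.2 points, up to 0.10 × 0.20 × 0.90 = 1.8 points.
- True VE 20%: 0.80 × 0.02 × 0.90 = 1.4 points, up to 0.80 × 0.20 × 0.90 = 14.4 points.

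**Step 4. The primary analysis.** Its cases are already cleared of wart-only detections, so the triggers of 19 and 29 cases, the two-sided alphas of 0.0204 and 0.0411, and the power in Table 7 do not move.

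**The case against.** The best defence is that the SAP is silent here, not contrary. ALL CIN 2/3, the CIN 1-or-worse endpoints and the any-CIN procedures all borrow the primary analysis methodology, and a reader could take the exclusion to travel with it. This does not settle the matter. III.C.3.e points back to methodology already described, and what III.C.1 describes is the exact, person-time analysis, with no wart rule. The rule comes later, in VII.D.1.e.1, and states its own scope.

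The mandatory Pap-based triage also limits wart-only colposcopy. That stands as a reason to expect a small share, but VII.D.1.e.1 was written with that triage in place and still found an exclusion necessary.

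Two stronger readings are tempting and should be resisted. A reader might infer that every exploratory CIN endpoint keeps the bias. The by-type and time-to-event analyses are on the primary endpoint, so that goes too far. A reader might also start from zero true efficacy, which with VEw = 90% gives 1.8 to 18.0 points. No planned CIN efficacy endpoint is confined to types outside the vaccine, and the Executive Summary attributes about 70% of high-grade dysplasia to HPV 16 and 18, so zero is a poor match, above all for ALL CIN 2/3.

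One further objection stands. A biopsy or excision avoided because warts were prevented can be a real effect on procedure burden, so removing wart-only events from the any-CIN procedure counts is debatable.

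**Conclusion.** The point holds as a gap in scope. The exclusion and its sensitivity analysis are narrower than the bias they answer. Wart-only CIN 1 is not removed from the secondary biopsy endpoint on the natural reading, no text extends the rule to the exploratory CIN 1-or-worse and all-CIN endpoints, and coverage of ALL CIN 2/3 turns on a label the SAP gives two ways. That last mismatch shows ambiguity and is not itself evidence of bias.

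The bias is potential. It needs both efficacy against warts and some wart-only colposcopies, and its size cannot be known from the SAP. Under the assumed ranges it is negligible for type-specific endpoints with true efficacy near 90%, and matters only for broad endpoints where true efficacy is low and the wart-only share is appreciable. The secondary objective is one of estimation and the exploratory endpoints concerned carry no formal test. The plan should be changed because the change is cheap and extends the sponsor's own rule; the primary conclusion is not at risk.

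**What to change.** In VII.D.1.e.1:

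- Apply the wart-only exclusion, with the same scheduled-visit Pap rule, to CIN of any grade in the secondary HPV 16/18-related biopsy and definitive-therapy endpoints, and in the exploratory ALL CIN 2/3, CIN 1-or-worse and all-CIN endpoints.
- Report the inclusive counts for each as the sensitivity analysis, as already planned for CIN 2/3 or worse.
- Show colposcopy and any-CIN biopsy and therapy both with and without wart-only colposcopies, so that an effect on procedure burden can be told apart from an effect on lesions.
- Say that the by-type and time-to-event analyses use the primary case set.

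Give ALL CIN 2/3 one classification and align the Executive Summary, I.B.5 and III.A.

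The cost is a few sentences. The Pap-based rule for identifying wart-only colposcopies already exists for the primary analysis. The downside is slightly fewer events and possibly lower efficacy estimates.

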For the exploratory efficacy estimates regarding CIN 1, CIN 2/3 and cervical cancer due to any cause, again only subjects who are HPV 16 seronegative by RIA at enrollment and HPV 16 PCR-negative from enrollment through Month 7 will be eligible to be counted as cases of HPV 16-related CIN 2/3 or cervical cancer. The same rules apply for HPV 18. For HPV types 31, 33, 35, 45, 51, 52, 55, 56, 58, 59, and 68, only subjects who are PCR-negative from enrollment through Month 7 for a given HPV type will be eligible to be counted as cases of CIN 1, CIN 2/3, or cervical cancer related to that type. No baseline serology testing will be performed for these 11 high-risk HPV types. Therefore, all subjects who are PCR-negative from enrollment through Month 7 for 1 of the types, even though they may be baseline seropositive for that type, will be eligible to be counted as cases of CIN 1, CIN 2/3, or cervical cancer related to that type. (This approach is conservative, since subjects who have baseline positive serology for a given HPV type have already mounted an immune response to that type.) With respect to disease endpoints related to high-risk HPV types that are not among the 13 listed above, subjects who meet criteria (1) and (3) through (7) above, have normal Pap results from Day 1 through Month 7, and have a history of normal Pap test results will be eligible to meet the case criteria. A sensitivity analysis will be performed in which all subjects who meet criteria (1) and (3) through (7) above (regardless of Pap test results from Day 1 through Month 7 and Pap history) will be eligible to meet the case criteria.

Modified Intention-to-Treat Populations

The first MITT analysis will include all subjects who are seronegative at enrollment and PCR-negative from enrollment through Month 7 to the appropriate HPV types, who receive all 3 vaccinations, and who have any follow-up visit following Month 7. The primary difference between this population and the per-protocol population is the inclusion of general protocol violators.

B. Study Participant Populations for Efficacy Analyses (Cont.)

The second MITT analysis will include all subjects who are seronegative and PCR-negative at enrollment to the appropriate HPV types, who receive at least 1 dose of quadrivalent HPV (Types 6, 11, 16, and 18) L1 VLP vaccine or placebo, and who have any follow-up visit after 1 month following the first injection.

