A sensitivity analysis will be performed in which cervical biopsies and tissue specimens collected outside the study (i.e., not according to protocol-specified procedures) are included in the “all CIN 2/3” efficacy analysis if they meet the case criteria. A cervical biopsy or tissue specimen that is collected outside the study will be eligible to be counted as an endpoint for this analysis *only* if a pathology panel diagnosis is available for the specimen.

b. Supplementary Summaries of the Primary Endpoints

The vaccine efficacy with respect to the primary endpoint will be summarized by HPV type. A point estimate of the vaccine efficacy will be provided along with a 95% confidence interval using the methodology described above for the primary analysis. These estimates will be provided for descriptive purposes only in the per-protocol and all of the MITT populations. No statistical testing will be conducted.

In addition, to assess the impact of the vaccine on HPV 16/18-related CIN 2/3 as diagnosed by a laboratory whose purpose is to provide pathologic diagnoses for patient management, a sensitivity analysis will be conducted in which the central laboratory (b)(4) diagnosis rather than the pathology panel diagnosis of each biopsy is used for case identification. Cervical biopsies and tissue specimens collected outside of the study will be included in this analysis if a local laboratory diagnosis and PCR results are available. Since these specimens were collected outside of the study, the local laboratory diagnosis will be used to identify cases rather than a central laboratory (b)(4) diagnosis. This analysis will be performed in the per-protocol and the first MITT population.

c. Time-to-Event Distributions

For the primary endpoint, survival analysis techniques will be used to compare the time-to-event (or disease-free time) distributions between

C. Approaches to Efficacy Analysis (Cont.)

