With respect to counting cases of CIN 2/3 and cervical cancer for the efficacy analyses, if a subject has a biopsy, ECC, or LEEP/conization specimen collected during the efficacy evaluation phase (post-Month 7) and the PCR result or pathology panel diagnosis is missing for the specimen, then the subject cannot be classified as a case based on that specimen.

When the missing data are needed to establish a subject's eligibility for analysis, the following rules will apply:

- With respect to missing serology results, subjects who are missing a baseline RIA result for a particular vaccine HPV type *will not* be eligible to be classified as cases of CIN 2/3 or cervical cancer related to that HPV type in the primary analysis.
- With respect to missing PCR results for cervicovaginal specimens, a subject's eligibility for analysis depends on the number of missing results. In Protocol 015, the PCR results for 2 cervicovaginal specimens collected at enrollment and 2 cervicovaginal specimens collected at Month 7 are used to determine each subject's eligibility for analysis. Subjects who are missing one or both of the PCR results for a given vaccine HPV type at enrollment or Month 7 will not be eligible to be cases of CIN 2/3 or cervical cancer related to that HPV type in the primary analysis.
- If the PCR result from a biopsy sample taken between enrollment and Month 7 (inclusive) is missing for a given vaccine HPV type, and the biopsy is diagnosed as abnormal, the subject *will not* be eligible to be classified as a case of CIN 2/3 or cervical cancer related to that type. If the PCR result is missing and the diagnosis is normal, the subject *will* be eligible. This rule was established because abnormal tissue is likely to be HPV PCR positive.

Similar rules will be applied for the secondary analysis.

Missing data which results from a subject dropping out of the study will be treated as missing (non-existent) in the primary analysis. However, a sensitivity analysis will be conducted in which the number of cases expected among subjects who are lost to follow-up will be projected assuming that these subjects would have been classified as cases with the same probability as those subjects who were not lost to

D. Statistical Methods (Cont.)

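### As worded, the rule in SAP VII.D.1.f that a specimen without PCR cannot make a case also removes panel-confirmed in-study lesions from the exploratory any-HPV-type CIN 2/3 endpoint, while outside-study specimens face no stated PCR condition

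*SAP*

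**What the plan says.** Section VII.D.1.f introduces its rule on specimens taken after Month 7 with "With respect to counting cases of CIN 2/3 and cervical cancer for the efficacy analyses" and continues that if "the PCR result or pathology panel diagnosis is missing for the specimen, then the subject cannot be classified as a case based on that specimen". No endpoint is exempted. The eligibility bullets that follow concern vaccine types, and two of the three name the primary analysis. A closing line extends similar rules to the secondary analysis. Exploratory analyses are not mentioned.

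The any-type endpoint is introduced in Section III.A: "Of primary exploratory interest is the overall incidence of ALL CIN 2/3 and invasive cervical cancer (caused by any vaccine or non-vaccine HPV type". Section III.C.3.a estimates it by the primary methodology, with a confidence interval and no test.

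Section III.B makes eligibility for this endpoint type-specific. For the 11 tested non-vaccine types, "only subjects who are PCR-negative from enrollment through Month 7 for a given HPV type will be eligible". HPV 16 and 18 also require seronegativity at enrollment. For high-risk types outside the 13 tested, the woman needs normal Pap results through Month 7 and a normal Pap history.

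For specimens collected outside the study, Section III.C.1 admits a specimen to the sensitivity analysis of the primary endpoint only with both HPV 16/18 PCR results and a panel diagnosis. The parallel analysis in Section III.C.3.a says such specimens "are included in the “all CIN 2/3” efficacy analysis if they meet the case criteria" and that a specimen "will be eligible to be counted as an endpoint for this analysis *only* if a pathology panel diagnosis is available for the specimen". PCR is not named there.

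**The concern.** A PCR requirement is part of the definition of an HPV 16/18-related lesion. It is not part of the definition of CIN 2/3 of any HPV type, where PCR serves only to show whether the woman was eligible for the type that caused the lesion. A single rule for both endpoints discards lesions that the panel has confirmed and that would count whichever high-risk type was found.

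Two things are at stake for the any-type endpoint. Some valid cases may be lost from the main analysis. And the outside-specimen sensitivity analysis cannot be read cleanly if it relaxes the PCR requirement for outside specimens while keeping it for in-study ones.

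**Working it through.** No figure in the plan depends on this point, so there is none to reproduce. The check is a comparison of texts, followed by an illustration of size under stated assumptions.

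**1. When does PCR matter for any-type eligibility?** Take a woman who is seronegative for HPV 16 and 18 at enrollment, PCR-negative for all 13 tested types through Month 7, and has the normal Pap record of III.B. She otherwise meets the per-protocol criteria. If her lesion contains a tested type, she is eligible for that type. If it is due to a high-risk type outside the 13, the Pap route makes her eligible. The PCR result cannot change her any-type eligibility. For a woman positive for some tested type at baseline or Month 7, it can, because III.B does not let her count for that type.

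**2. Who counts, reading VII.D.1.f literally and III.C.3.a as stated?** For a woman eligible for every type, with panel-confirmed CIN 2/3:

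| Specimen | Main any-type analysis | III.C.3.a sensitivity analysis |
|---|---|---|
| In-study, PCR available | counts | counts |
| In-study, PCR missing | excluded | excluded |
| Outside, PCR available | excluded | can count |
| Outside, PCR missing | excluded | can count |

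Moving from the main to the sensitivity analysis adds outside specimens and also drops the PCR condition for them alone. The corresponding analysis of the primary endpoint in III.C.1 keeps PCR for outside specimens, so there only the source changes.

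**3. Is the last row of the table a real possibility?** Yes. Section I.B.1 lists outside specimens with a local diagnosis and a panel diagnosis but no PCR as one of the situations expected.

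**4. Size.** The plan gives neither the share *m* of CIN 2/3 specimens without a PCR result nor the any-type case count, so both are assumed. If every such specimen cost a case, counted cases = (1 − *m*) × true cases. With equal *m* in both arms, the variance of the log rate ratio, about 1/C_v + 1/C_p, is multiplied by 1/(1 − *m*):

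- *m* = 2%: 1/0.98 = 1.020, standard error up 1.0%
- *m* = 5%: 1/0.95 = 1.053, standard error up 2.6%
- *m* = 10%: 1/0.90 = 1.111, standard error up 5.4%

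These are upper bounds on the loss, because a woman may qualify on other tissue.

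**5. Bias.** Assume 36 vaccine and 60 placebo cases with equal follow-up. Then efficacy = 1 − 36/60 = 40.0%, with exact 95% interval 7.8% to 61.4% by the plan's own method. With equal missingness the expected value stays at 40%. With unequal missingness, expected efficacy is 1 − 0.6 × (1 − m_v)/(1 − m_p):

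- 10% missing in vaccine, 5% in placebo: 1 − 0.6 × 0.90/0.95 = 43.2%
- 5% missing in vaccine, 10% in placebo: 1 − 0.6 × 0.95/0.90 = 36.7%

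**The case against.** The strongest reply is that the rule was meant only for the HPV 16/18 endpoints. The bullets around it concern vaccine types and mention the primary and then the secondary analysis. Section III.C.3.b also counts cases on the central laboratory diagnosis instead of the panel's, which suggests that the rule was not meant to bind every analysis. On that reading nothing is lost. It is plausible, but it is not written. The sentence covers the efficacy analyses as a whole, III.C.3.a borrows the primary methodology, and the Executive Summary lists all CIN 2/3 as of secondary interest although III.A calls it exploratory.

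A second reply is that the case-criteria clause in III.C.3.a may bring the PCR requirement back for outside specimens. In-study and outside specimens would then be treated alike, but panel-confirmed lesions without PCR would be lost from both. The contrast with III.C.1, which names PCR expressly, would serve no purpose.

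Three stronger inferences are not supported:

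- A reader might infer that III.C.3.a admits an outside lesion without PCR from a woman who was HPV 16-positive at Day 1. The panel diagnosis is a minimum there, not a sufficient condition. She must also meet the case criteria, and those are type-specific.
- A reader might infer that a woman whose biopsy fails PCR is simply treated and lost. VII.D.1.f bars only that specimen. Excised tissue also goes for PCR and to the panel, and VII.D.1.e.2 counts her if it qualifies.
- A reader might infer harm to the combined analysis of Protocols 005, 007, 013 and 015. That analysis has its own plan, which is not at hand, and Section VI.A expects continued follow-up to yield enough cases for it.

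**Conclusion.** The point holds as a minor fault in the wording of VII.D.1.f. The sentence does not limit its PCR condition to type-specific endpoints. Taken as written, it drops valid any-type cases among women eligible for every type, and it makes the III.C.3.a sensitivity analysis hard to interpret.

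The consequence is confined to an exploratory endpoint that is estimated without a test, and to a sensitivity analysis of it. The primary HPV 16/18 result and the case counts that trigger the interim and final analyses do not change. The loss of cases cannot exceed the missing-PCR share if that share is taken over women who would be any-type cases, and nothing in the plan suggests that it differs by arm. The percentages and case counts used to show size are assumptions, not figures from the plan.

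**What to change.** In VII.D.1.f, limit the PCR part of the specimen rule to type-specific endpoints. For any-type endpoints, add that a specimen counts on the panel diagnosis alone when the woman is eligible for all 13 tested types and has the normal Pap record of III.B, and that otherwise a PCR result is needed to establish eligibility. Refer to this rule in III.C.3.a for both the main analysis and the outside-specimen sensitivity analysis, so that the two differ only in specimen source.

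The cost is a few lines of text and a small programming change, with no new data. The drawback is that a few any-type cases will have no assigned HPV type; their number should be reported by arm.
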